1.4.3 Discussion

BI 767551 is currently under evaluation in Phase I in healthy volunteers and ambulatory COVID-19 patients. It is not yet known whether its administration results in beneficial clinical effects. In SARS-CoV-2-infected subjects, administration of BI 767551 may reduce the risk of progressing to severe disease and contribute to accelerated viral clearance.

Several other SARS-CoV-2-neutralizing antibodies are under clinical development. Recently, two new therapies (*Bamlanivimab* by **Casirivimab** in combination with Imdevimab by **Casirivimab**) have gained FDA-authorization for emergency use for the indication of mild-tomoderate COVID-19 in adults and pediatric patients (12 years and older) with a positive COVID-19 test, who are at high risk for progressing to severe COVID-19 and/or hospitalization.

Antibody-dependent enhancement cannot be ruled out completely, but the risk is considered low that BI 767551 increases the risk of progression of COVID-19 based on preclinical studies. Rather, by targeting the receptor-binding domain of the SARS-CoV-2 spike (S) protein with high affinity and by not blocking the ACE-2 receptor, BI 767551 neutralizes SARS-CoV-2, preventing infection and increasing clearance thereby reducing the risk of severe disease.

Hypersensitivity reactions are anticipated adverse effects. In addition, although no human antigen target is described for BI 767551, all trial subjects will be carefully monitored for any unspecific effects. As described in this section, this and other theoretical risks associated with BI 767551 will be monitored along with a mitigation plan.

The data will be evaluated between the first (Phase II) and second (Phase III) parts to ensure that the antibody can perform as expected regarding increase in viral clearance. Only then will the study proceed to the larger Phase III portion. In addition, an Independent DMC will monitor subject's safety and BI 767551 efficacy during the the trial. In case BI 767551 does not demonstrate a potential for efficacy (interim futility analysis), the study may also be recommended to be stopped by the DMC.

Taking into account current knowledge of nonclinical data and relevant anticipated effects, BI 767551 has currently a positive Benefit-Risk profile for the treatment of patients with mild to moderate COVID-19 symptoms.

2. TRIAL OBJECTIVES AND ENDPOINTS

2.1 MAIN OBJECTIVES, PRIMARY AND SECONDARY ENDPOINTS

2.1.1 Main objectives

This trial has two sequentially enrolling parts with different objectives.

The overall objective of this trial is to evaluate the concept of pharmacological activity of BI 767551 in non-hospitalized patients with mild to moderate COVID-19 symptoms and to identify a potentially efficacious and safe dose regimen from Phase II part to take into the Phase III part.

The Phase II part of the trial will aim to prove the concept of pharmacological activity of different dose levels and routes of administration of BI 767551 in comparison to placebo and to identify efficacious and safe dose regimens in non-hospitalized patients with mild to moderate COVID-19 symptoms. The primary objective is to numerically compare the BI 767551 dose levels and routes of administration to placebo for the ratio of the time-weighted change from baseline in viral shedding over 8 days. The primary treatment comparison will be as treated, including all data prior to start of any other treatment with a similar mode of action that has proven efficacy (either preliminary via EUA by FDA or via full approval by the FDA or EMA).

Secondary objectives of Phase II are to numerically compare the BI 767551 doses and routes of administration to placebo for virological outcomes.

The Phase II part of the trial will support the decision on whether to move to Phase III and which dose level and route of administration to take to the Phase III part of the study. The IV route of administration has been shown to be efficacious in development programs for other neutralizing antibodies however, the inhaled route of administration is a convenient, novel route of delivery and more directly addresses lung infection. If shown to be efficacious in Ph II, the protocol may be amended to select the inhaled route of administration to be carried forward into Ph III.

The Phase III part of the trial will aim to confirm efficacy, safety and tolerability of the dose regimen of BI 767551 selected from the Phase II part in comparison to placebo in non-hospitalized patients with mild to moderate COVID-19 symptoms. The primary objective is to demonstrate superiority of the BI 767551 dose regimen for the difference in the proportion of patients hospitalized or death from any cause over 29 days. The primary treatment comparison will be performed on all randomised patients, including all data prior to start of any other treatment with a similar mode of action that has proven efficacy (either preliminary via EUA by FDA or via full approval by the FDA or EMA).

Secondary objectives of Phase III are to numerically compare the BI 767551 dose regimen to placebo for virological and other clinical outcomes.
2.1.2 **Primary endpoint(s)**

The primary endpoint in Phase II is the time-weighted change from baseline in viral shedding over 8 days in site collected nasopharyngeal (NP) swabs by RT-qPCR, defined as a change from baseline in \log_{10} viral load. Refer to Section 7.2.3 for further details.

The primary endpoint in Phase III is hospitalization or death from any cause by Day 29.

2.1.3 Secondary endpoint(s)

2.1.3.1 Secondary endpoints in Phase II

The secondary endpoints in Phase II are:

- Time-weighted change from baseline in viral shedding over 29 days in site collected NP swabs by RT-qPCR, defined as a change from baseline in log₁₀ viral load.
- Loss of detection of SARS-CoV-2 RNA by site collected NP swab at Day 4, 8, 15, 22 and 29.

2.1.3.2 Secondary endpoints in Phase III

The secondary endpoints in the Phase III are:

- Time to death over 29 days
- Hospitalization by Day 29
- Hypoxia or hospitalization or death from any cause by Day 29
- Hypoxia by Day 29
- Time to clinical improvement over 29 days, defined as the time to either an improvement of two points on the 11-point WHO Clinical Progression Scale or a score of 0 on the Clinical Progression Scale, whichever comes first (see Section 5.1.2).
- Time to loss of detection of SARS-CoV-2 RNA by site collected NP swabs over 29 days

20 Apr 2021

33563257-02Clinical Trial ProtocolPage 38 of 127Proprietary confidential information © 2021 Boehringer Ingelheim International GmbH or one or more of its affiliated companies

20 Apr 2021

33563257-02Clinical Trial ProtocolPage 39 of 127Proprietary confidential information © 2021 Boehringer Ingelheim International GmbH or one or more of its affiliated companies

33563257-02Clinical Trial ProtocolPage 40 of 12Proprietary confidential information © 2021 Boehringer Ingelheim International GmbH or one or more of its affiliated companies

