3.3.1 Main diagnosis for trial entry

Please refer to Section 8.3.1 (Source Documents) for the documentation requirements pertaining to the in- and exclusion criteria.

Eligibility criteria for Phase II and Phase III are the same. Patients participating in Phase II are not eligible for Phase III. The trial will include non-hospitalized patients with mild to moderate COVID-19.

The trial will also include patients with mild to moderate COVID-19 symptoms that are at high risk for progression of disease due to underlying cardiovascular or respiratory disease, diabetes, chronic kidney disease, or other comorbidities, and immunocompromised persons (e.g., HIV-infected patients, organ transplant recipients, or patients receiving cancer chemotherapy) as long as they do not meet other exclusion criteria. See Section 7.4 for the definition of high risk patients.

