3.3.2 Inclusion criteria

- 1. \geq 18 years old, males and females.
- 2. Signed and dated written informed consent in accordance with ICH-GCP and local legislation prior to admission to the trial.
- 3. Documentation of laboratory-confirmed SARS-CoV-2 infection, as determined by a molecular test (antigen or nucleic acid) from any respiratory tract specimen (NP or nasal swab or saliva) collected no more than 72 hours prior to start of treatment.
- 4. Patients experienced mild to moderate COVID-19-related symptoms or measured fever for no more than 5 days prior to start of treatment where symptoms are defined by fever, feeling feverish, fatigue, cough, shortness of breath at rest or during activity, sore throat, body pain or muscle pain/ aches, chills, headache, nasal obstruction or congestion, loss of smell or taste, nausea, diarrhea, vomiting, or dysgeusia.

- 5. One or more of the following signs/symptoms present on day of start of treatment: fever, feeling feverish, fatigue, cough, shortness of breath at rest or during activity, sore throat, body pain or muscle pain/ aches, chills, headache, nasal obstruction or congestion, loss of smell or taste, nausea, diarrhea, vomiting, or dysgeusia.
- 6. Women of childbearing potential (WOCBP)¹ and men able to father a child must be ready and able to use highly effective methods of birth control per ICH M3 (R2) that result in a low failure rate of less than 1% per year when used consistently and correctly. A list of contraception methods meeting these criteria is provided in Section 4.2.2.3.

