5.1.2 Improvements on the WHO Clinical Progression Scale

The following 11-point WHO Clinical Progression Scale will be used for the assessment of Clinical improvement (Figure 5.1.2:1):

Boehringer Ingelheim BI Trial No.: 1487-0001 c33563257-02

Clinical Trial Protocol

Proprietary confidential information © 2021 Boehringer Ingelheim International GmbH or one or more of its affiliated companies

Figure 5.1.2:1

WHO Clinical Progression Scale [R20-2002]

Patient State	Descriptor	Score
Uninfected	Uninfected; no viral RNA detected	0
Ambulatory mild disease	Asymptomatic; viral RNA detected	1
	Symptomatic; independent	2
	Symptomatic; assistance needed	3
Hospitalised: moderate disease	Hospitalised; no oxygen therapy*	4
	Hospitalised; oxygen by mask or nasal prongs	5
Hospitalised: severe diseases	Hospitalised; oxygen by NIV or high flow	6
	Intubation and mechanical ventilation, pO_2/FiO_2 ${\simeq}150$ or SpO_2/FiO_2 ${\simeq}200$	7
	Mechanical ventilation pO_/FIO_ <150 (SpO_/FiO_ <200) or vasopressors	8
	Mechanical ventilation $pO_{\rm 2}/{\rm FiO_2}$ <150 and vasopressors, dialysis, or ECMO	9
Dead	Dead	10

Figure: WHO clinical progression scale

ECMO=extracorporeal membrane oxygenation. FiO₂=fraction of inspired oxygen. NIV=non-invasive ventilation. pO₂=partial pressure of oxygen. SpO₂=oxygen saturation. *If hospitalised for isolation only, record status as for ambulatory patient.

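### For patients entering at WHO score 2, the Phase III endpoint of time to clinical improvement requires RNA negativity, so symptom resolution with RNA still detected never counts, although it does count for patients entering at score 3

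*Protocol*

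**What the plan says.** Protocol Section 2.1.3.2 lists time to clinical improvement over 29 days as a Phase III secondary endpoint. The event is an "improvement of two points on the 11-point WHO Clinical Progression Scale or a score of 0", whichever is reached first. The same list has a separate endpoint for time to loss of RNA detection in site-collected nasopharyngeal swabs, also over 29 days.

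The lower end of the scale in Section 5.1.2 reads:

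- Score 0: "Uninfected; no viral RNA detected"
- Score 1: "Asymptomatic; viral RNA detected"
- Score 2: "Symptomatic; independent"
- Score 3: "Symptomatic; assistance needed"

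Scores 4 to 9 are for hospitalised patients. A footnote has patients hospitalised only for isolation scored as ambulatory.

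Two statements fix the entry scores. Section 3.3.1 says: "The trial will include non-hospitalized patients with mild to moderate" COVID-19. Inclusion criterion 5 (Section 3.3.2) requires: "One or more of the following signs/symptoms present on day of start of treatment".

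Section 7.2.4 analyses time-to-event secondary endpoints with a Cox model and a log-rank test, with nominal p-values. The SAP covers Phase II only (Section 3) and adds nothing on this endpoint.

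**The concern.** An endpoint named clinical improvement should respond when a patient's symptoms resolve. Here the response depends on the entry score. Two patients who reach the same state, symptom-free with RNA still detected, are classified in opposite ways, and the one who started in the worse category is the one counted as improved.

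For a score-2 entrant whose symptoms resolve before RNA is lost, the event is postponed until RNA loss. If RNA persists to Day 29, the patient stays event-free. A favourable hazard ratio could then reflect faster viral clearance but be reported as clinical benefit, and a real symptom benefit could be masked by prolonged RNA positivity. Section 2.1.1 names virological and clinical outcomes as separate things to compare, and this definition blurs them.

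**Working it through.** The documents give no event rate, power or baseline split for this endpoint, so there is no figure to reproduce. The check enumerates the definition; an illustration with assumed inputs follows.

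**Step 1: entry scores.** Symptoms on the day of treatment rule out scores 0 and 1, and non-hospitalised status rules out 4 and above. This leaves 2 and 3.

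**Step 2: apply the rule.** Event if (entry score − current score) ≥ 2, or current score = 0. Improvement is taken as relative to the entry score.

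| Entry | Current | Drop | State reached | Event? |
|---|---|---|---|---|
| 2 | 1 | 1 | symptom-free, RNA detected | no |
| 2 | 0 | 2 | RNA not detected | yes |
| 3 | 2 | 1 | symptomatic, independent | no |
| 3 | 1 | 2 | symptom-free, RNA detected | yes |
| 3 | 0 | 3 | RNA not detected | yes |

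Rows one and four are the same end state with opposite results. RNA negativity is necessary for 100% of score-2 entrants and is not necessary for score-3 entrants.

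**Step 3: the score-0 clause.** From 2, score 0 is already a two-point drop. From 3, score 1 already qualifies. The clause would matter only for entry at score 1, which criterion 5 excludes, so it is redundant for eligible patients.

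**Step 4: overlap with time to loss of detection.** This depends on two things that the documents do not give: the split between entry scores 2 and 3, and the score of a patient who is RNA-negative but still symptomatic (the score-0 descriptor does not mention symptoms). An illustrative simulation used these assumptions:

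- visits at Days 4, 8, 15, 22 and 29;
- independent Weibull times (shape 1.8) to RNA loss and to symptom resolution, each with a median between 8 and 15 days.

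Overlap is the share of patients with both events at the same visit; neither event by Day 29 also counts as agreement.

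*Reading A: RNA negativity alone gives score 0.* For score-2 entrants the event time is the RNA-loss time, so overlap is 100%. With 70% to 90% entering at score 2, overall overlap is about 81% to 98%.

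*Reading B: score 0 also needs absence of symptoms.* For score-2 entrants the event time is the later of RNA loss and symptom resolution:

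| Median RNA loss (days) | Median symptom resolution (days) | Overlap, score-2 entrants |
|---|---|---|
| 15 | 8 | 84% |
| 15 | 11 | 74% |
| 11 | 11 | 63% |
| 8 | 15 | 35% |

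Under both readings no score-2 entrant can have the event before RNA loss. Under Reading A there is also an error in the other direction: a patient who is RNA-negative but still symptomatic counts as clinically improved.

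**The case against.** A reader might go further and infer that the endpoint cannot register symptom recovery at all. It can: 3 to 1 is symptom recovery with RNA present and counts, and a score-2 patient who both recovers and clears RNA also has an event. Only recovery from score 2 with RNA still detected is missed.

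A reader might also infer that the endpoint largely repeats the viral-clearance endpoint. The documents do not establish that. They give no split between scores 2 and 3, and under Reading B the event is a joint RNA-and-symptom one, with overlap as low as 35% in the illustration. They also do not say which swab feeds the score. In the flow chart the scale is recorded at Day 3, when no staff-collected nasopharyngeal swab is scheduled, so the two endpoints need not share every assessment.

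Nor can it be concluded that symptom recovery goes unmeasured. A daily diary runs to Day 29 (Protocol Section 6.2.3), the SAP refers to further endpoints (Section 4), and parts of the public protocol are withheld. Calling the affected patients wrongly censored would also be too strong, because under the protocol's own definition they are event-free.

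The score-0 clause is harmless. A patient randomised in error at score 1 would stay in the all-randomised analysis and could qualify only through it.

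Finally, the consequence is limited: there are no key secondary endpoints, secondary p-values are nominal, and the two-point wording is conventional. These limits stand. None of them changes the opposite treatment of 2 to 1 and 3 to 1.

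**Conclusion.** The point holds in this form. For score-2 entrants the endpoint is met only through RNA negativity, and symptom resolution with RNA still detected never counts, while that same state counts for score-3 entrants. This follows from the protocol's definitions alone, reading improvement as relative to the entry score.

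The size is exact for the requirement (all score-2 entrants) and open for the overlap with time to loss of detection. The 35% to 100% range for score-2 entrants comes from assumed event times and from two readings of score 0, and is not an estimate for this trial. The share of patients affected is the unstated proportion entering at score 2.

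This is a defect in a secondary endpoint and bears on interpretation. Type I error, the primary analysis and the sample size are untouched. The SAP (Section 4) reports that the study was discontinued with 5 patients randomised, so the practical value lies in the protocol text and any reuse of it.

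**What to change.** Define clinical improvement for all patients as the first assessment at which the patient is asymptomatic: WHO score 1, or score 0 with no symptoms, regardless of RNA result. State that an RNA-negative patient who still has symptoms is not counted as improved. Changing the threshold to score 1 or lower without that sentence would not be enough, because the score-0 descriptor is silent on symptoms. Leave RNA loss to its own secondary endpoint, and drop the score-0 clause.

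Two clarifications belong with this. Name the swab result that separates score 0 from score 1. Also state whether the risk covariate enters the Cox model: Section 7.2.4 adds it only to endpoints not based on viral load, and it is unclear on which side the present definition falls. The revised endpoint would clearly be non-virological.

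The cost is wording plus a short scoring rule, since the scale is already collected at the visits. The downside is a departure from the conventional two-point wording; the two-point definition can be kept as a supportive analysis. No multiplicity adjustment is affected.

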3. DESCRIPTION OF DESIGN AND TRIAL POPULATION

3.1 OVERALL TRIAL DESIGN

This is a Phase II/III seamless, randomised, double-blind, placebo controlled, parallel group, design study to evaluate efficacy, safety and tolerability of BI 767551 for the treatment of symptomatic, non-hospitalized adults with mild to moderate COVID-19.

The study comprises two parts in an operationally seamless design. The exploratory Phase II part will assess viral load measures of SARS-CoV-2 RNA by NP swab to evaluate the neutralizing mode of action (MoA) of BI 767551 and provide data to select the dose level or dose regimen also considering safety and tolerability to take into the Phase III portion should there be adequate neutralizing ability. Phase II includes both inhaled and i.v. routes to explore neutralizing potential, safety and PK to provide a comparison against Placebo of doses and routes ahead of decision of dose and route for the Phase III portion. For more details please see Section 4.1.2.

The confirmatory Phase III part of the study will investigate clinical outcomes for events of hospitalization or death throughout a 29 day period and further assessment of safety and tolerability for one dose regimen vs placebo. The patients will be followed for a 90-day observation period to assess any long-term outcomes from patients.

In Phase III, randomisation will be stratified by "high" versus "low" risk of progression to COVID-19. This is to ensure equal distribution of patients in these two groups to each treatment group. There is no minimum number of "high" risk patients for this study. For the definition of "high" and "low" risk please refer to Section 7.4.

Patients will be enrolled (screened) in the trial once the appropriate informed consent has been obtained. At the start of the trial, patients who successfully complete screening and still meet the inclusion/exclusion will be randomised in Phase II in a 2:2:2:1 ratio to one of the four arms:

- Single placebo i.v. infusion with placebo inhalation
- Single low dose 10 mg/kg of BI 767551 i.v. infusion with placebo inhalation
- Single high dose 40 mg/kg of BI 767551 i.v. infusion with placebo inhalation
- Single placebo i.v. infusion with inhalation 250 mg of BI 767551

3.2 DISCUSSION OF TRIAL DESIGN, INCLUDING THE CHOICE OF CONTROL GROUP(S)

This seamless, trial design, with separate exploratory Phase II and a confirmatory Phase III, will include pre-defined decision criteria for continuing BI 767551 dose and selecting the dose regimen from Phase II into Phase III (see Section 3.1), with the intent of ensuring that a positive

Boehringer Ingelheim		
BI Trial No.: 1487-0001		20 Apr 2021
c33563257-02	Clinical Trial Protocol	Page 43 of 127

proof of concept of pharmacological activity will quickly be followed by the confirmation of clinical efficacy and safety of BI 767551.

A parallel group, randomised, seamless, double-blind, placebo controlled, design trial was considered most appropriate to assess the efficacy and safety of BI 767551 in symptomatic, non-hospitalized adults with mild to moderate COVID-19 symptoms.

Phase II will aim to prove the concept of pharmacological activity and dose/exposure-response relationship, and thus to select the dose regimen for Phase III of this trial. Phase III will investigate the most efficacious, tolerable and safe dose regimen from the Phase II regimens, unless an unexpected safety or efficacy finding requires dose modification beyond the prespecified transition scenarios in Section 3.1.

A control placebo group is included in this study to reduce bias with regard to the treatment dependent effects and to preserve the integrity of the assessments of safety and efficacy. The control arm reduces the subjective bias in completion of symptom diaries by participants.

A DMC, which is independent of the sponsor will be established for this study to assess safety on an ongoing basis throughout the study (see Section 8.7). The DMC members will perform ongoing safety surveillance and provide recommendations to the sponsor regarding study conduct. The DMC will also assess efficacy at two planned interim analyses (See Section 7.2.8). Futher details are provided in the DMC charter.

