4.1.2 Selection of doses in the trial and dose modifications

A viral dynamic model, based on the influenza A model developed by Baccam et al. was used in combination with a pharmacokinetic model to predict the human efficacious dose [R20-3336] (refer to n00282535 and Section 1.2.2 for further details).

In the 1487-0001 study, patients will receive treatment no more than 5 days after symptom onset. For this later treatment start, which is considered a more realistic scenario in clinical practice, the viral dynamics model indicates that the maximum obtainable response in the model is smaller than with treatment onset at symptom onset. In addition, the maximum obtainable response is less sensitive to dose (i.e. no relevant difference between e.g. 40 mg/kg and 10 g/kg). Therefore,

Boehringer Ingelheim		
BI Trial No.: 1487-0001		20 Apr 2021
c33563257-02	Clinical Trial Protocol	Page 53 of 127

a lower i.v. dose (10 mg/kg) may show comparable efficacy as the higher (40 mg/kg) i.v. dose in clinical practice and is therefore included in Phase II.

For inhalational administration, a single dose of 250 mg is predicted to be efficacious. Assuming 6-30% deposition in the lower airway,

. Given the novelty and uncertainty in pharmacokinetics for inhaled delivery of antibody therapeutics and their use in the treatment of respiratory viruses, the efficacious dose was selected as the maximum feasible dose 250 mg.

To account for emerging variants, IC₅₀ values were incorporated into the mechanistic viral dynamic PK/PD model and scanned across a range from 1.5 to 15000 ng/mL, assuming a hill slope of 1.

Dose for inhalation:

Following inhalative administration, maximum exposure in ELF is reached immediately at the end of the inhalation, predicted peak concentrations in ELF are about

potentially leading to faster onset of action and more rapid

virus neutralization.

Simulated BI 767551 ELF concentrations for a single inhaled dose of BI 767551 were compared to live virus 100% neutralizing concentrations (NC₁₀₀). After a single inhaled dose of 250 mg (assuming \geq 6% deposition in the lower airways), BI 767551 ELF concentrations were predicted

Clinical Trial Protocol

Proprietary confidential information © 2021 Boehringer Ingelheim International GmbH or one or more of its affiliated companies

to be greater than

c35245352].

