6.2.1 Screening and run-in period(s)

Screening Period

Once the patient has consented, the patient is considered to be enrolled in the trial. The patient should be recorded on the enrollment log and be registered in the IRT. Each patient will be assigned a unique patient number, via the IRT system and enrollment will be recorded in eCRF. For the schedule of assessments and procedures during the screening period refer to the Flowchart.

During the screening visit, demographics information will be collected. This includes:

- age on the day of informed consent (in years)
- Sex (male, female in order to describe the subject's sex at birth),
- For women: of childbearing potential yes / no in order to characterize the patient population and as a basis for contraception requirements
- Ethnicity and race in order to sufficiently characterize the patient population, to support possible subgroup analyses if needed and to support the calculation of the kidney function via the CKD EPI formula unless not acceptable according to local regulations.

Study requirements, including the procedure for the follow-up of prematurely withdrawn patients must be fully explained to the patient and written informed consent obtained prior to initiating any study-related evaluation. The importance of staying in the trial until completion of all study requirements will be emphasized. No trial procedures should be done unless the patient has consented to taking part in the trial.

SARS-CoV-2 infection documentation is recorded on the eCRF. Positive RT-qPCR or antigen test will be obtained prior to randomisation. Documentation of laboratory-confirmed SARS-CoV-2 infection as determined by molecular test from any respiratory tract specimen (NP, nasal swab or saliva) is also acceptable.

Patients will be asked about their first symptoms related to COVID-19 and their current symptoms. The time of symptom onset should be recorded.

Urine pregnancy testing should be done prior to administration of study drug for all women of childbearing potential. Study drug should only be administered in case of a negative test result.

Medical History:

The current medical history of the patient may not be sufficient to confirm eligibility for the trial and the investigator may need to request previous medical histories and evidence of any

Boehringer Ingelheim		
BI Trial No.: 1487-0001		20 Apr 2021
c33563257-02	Clinical Trial Protocol	Page 79 of 127

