7.2.3 Primary objective analyses

Primary endpoint analyses in Phase II

The primary endpoint of Phase II is defined in Section 2.1.2.

Viral load data will be log-transformed prior to analysis. Time-weighted average change in log₁₀ viral load from baseline is defined as:

$$\frac{\sum_{i=a}^{b-1} \{0.5 * (Y_i + Y_{i+1}) * (t_{i+1} - t_i)\}}{(t_b - t_a)}$$

Boehringer Ingelheim		
BI Trial No.: 1487-0001		20 Apr 2021
c33563257-02	Clinical Trial Protocol	Page 87 of 127

• Where

- a = baseline assessment at Day 1
- b = last assessment at or prior to the threshold day (Day 8 for the primary endpoint)
- Y_i = change from baseline in log₁₀ viral load at visit i (and where $Y_a=0$)
- t = time at the specified time point (the actual study day)

An analysis of covariance (ANCOVA) model with log_{10} baseline viral load and baseline serology status as covariates will be used. Adjusted means and 95% confidence intervals (CIs) will be provided by treatment group. The ratio of the mean time-weighted change from baseline in log_{10} viral load will be used to quantify the treatment effect, comparing each active treatment arm to placebo as the reference. Intercurrent events will be handled using the Primary strategy as defined in Section 7.2.2.

Primary endpoint analyses in Phase III

The primary endpoint of Phase III is defined in Section 2.1.2.

The cumulative proportion of patients hospitalized or dying by Day 29 will be estimated for each randomised group using Kaplan-Meier (KM) methods to take account of losses to follow-up. It will be estimated overall and within each stratum. The analysis will be stratified by "high" versus "low" risk of progression to severe COVID-19 and baseline serology status.

For patients with known event of hospitalization or death:

Time to hospitalization or death [days] = earlier date of hospitalization or death – date of randomisation + 1.

For patients with no known event of hospitalization or death or where censoring rules apply:

Time to hospitalization or death [days] = date of censoring – date of randomisation + 1.

Missing data are handled by using survival analysis techniques. Intercurrent events will be handled using the Primary strategy as defined in Section 7.2.2. For further details on censoring rules of the primary analysis, refer to Table 7.3.1:1.

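### The Phase II primary model omits the recorded interval from symptom onset to dosing, which the protocol's own viral model links to response, and the stated dose-response aim needs reconciling with that model

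*Protocol*

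**What the plan says.** Protocol 4.1.2 contrasts dosing at symptom onset with this trial's later start of up to 5 days. For the later start, "the maximum obtainable response in the model is smaller than with treatment onset at symptom onset". It adds that "the maximum obtainable response is less sensitive to dose", and gives the two i.v. levels as an example of no relevant difference (the lower level is printed there in g/kg, elsewhere in mg/kg). The lower i.v. dose was included because it "may show comparable efficacy as the higher (40 mg/kg) i.v. dose".

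On data collection, 6.2.1 states: "The time of symptom onset should be recorded". The same section puts the estimated date and time of first symptoms in the medical history.

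On analysis, 7.2.3 says of the Phase II primary ANCOVA that log10 "baseline viral load and baseline serology status as covariates will be used". Each active arm is compared with placebo. Under 7.2.4 the 29-day time-weighted endpoint is analysed in the same way. Section 7.4 uses no stratification in Phase II.

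On purpose, 3.2 states: "Phase II will aim to prove the concept of pharmacological activity and dose/exposure-response relationship, and thus to select the dose regimen for Phase III". It then says Phase III will study the most efficacious, tolerable and safe regimen. The synopsis rationale and 1.3 instead carry forward the lowest dose that is efficacious and safe.

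**The concern.** Two things do not fit together.

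1. **An unused baseline variable.** The sponsor's model makes delay from onset a driver of viral response, and the delay is known before dosing for every patient. Leaving it out of the model puts whatever variation it explains into the error term and leaves chance differences between arms uncorrected. Baseline viral load is only a partial substitute, because the same load can occur while the virus is rising or falling.

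2. **An aim at odds with the model.** Section 3.2 sets out to prove a dose/exposure-response relationship and to select the regimen from it, while 4.1.2 expects little between the two i.v. levels. If the most-efficacious wording were followed, a chance ordering of the i.v. arms could weigh in the choice. Under the lowest-efficacious wording it need not.

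**Working it through.** **Arm sizes.** 7.4 gives 112 patients at 2:2:2:1, then 88 of the 200 at 1:1:1:2.
- Placebo and each i.v. arm: 112×2/7 + 88×1/5 = 32 + 17.6 = 49.6.
- Inhaled arm: 16 + 35.2 = 51.2. This agrees with about 50 per arm.

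**The plan's own figure.** 7.5.1 states an 85% probability that the AUC ratio exceeds 1.4 with 50 per arm, and 2% if there is no difference. No between-patient SD is given, so it has to be calibrated. Treating the result as a ratio of two normal means,

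P(ratio > t) = Φ[(μA − t·μP) / ((σ/√n)·√(1+t²))], with μP = 1.25.

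- *Stated slopes*, μA = 1.25 + 0.85 = 2.10, with σ solved from the 85% cell: σ = 1.39. At 40/50/60 per arm this gives 82.3/85.0/87.2% (stated 81/85/88%). It gives 73.8% for ratio >1.5 at 50 per arm (stated 69%) and 6.9% under no difference (stated 2%).
- *μA and σ fitted to all 15 cells* of Table 7.5.1:1: μA = 2.01, σ = 1.04. Every cell is within about 1.5 points, and the no-difference value, not used in the fit, is about 2.5%.

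The second pair is used below, with the first as a sensitivity check. Both are calibrations, not independent reproductions.

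**Gain from the covariate.** Assume the onset interval explains a share R² of the residual variance left after viral load and serology. The SE is multiplied by √(1−R²), equivalent to 1/(1−R²) times the patients.

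| R² (assumed) | SE factor | Equivalent patients | P(ratio >1.4), n = 50 |
|---|---|---|---|
| 0 | 1 | 1 | Φ(0.26/0.253) = 84.8% |
| 0.05 | 0.975 | 1.05 | Φ(0.26/0.247) = 85.4% |
| 0.15 | 0.922 | 1.18 | Φ(0.26/0.233) = 86.7% |

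Here 0.26 = 2.01 − 1.4×1.25 and 0.253 = (1.04/√50)×√2.96. Fitting the AUC ratio itself as normal (mean 1.594, SE 0.188 at 50 per arm), a residual correlation of 0.5 (R² = 0.25) gives Φ[0.194/(0.188×√0.75)] = 88.3%.

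**Chance imbalance.** With an assumed SD of 1.0 to 1.7 days for the interval, the difference in mean interval between two arms of 50 has SD 1.0×√(2/50) = 0.20 to 1.7×√(2/50) = 0.34 days. The probability of a gap above half a day is 1 to 14%.

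**Ordering the two i.v. arms.**
- SE of the difference = 1.04×√(2/50) = 0.208.
- Difference detectable with 80% power (two-sided 5%) = 2.80×0.208 = 0.58, and 0.58/2.01 = 29% of the active mean.
- A true 5% difference (0.10) is ordered correctly with probability Φ(0.10/0.208) = 68%; no difference gives 50%.
- With σ = 1.39 and mean 2.10: SE 0.278, detectable difference 0.78 (37%), correct ordering Φ(0.105/0.278) = 65%.

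**The case against.** The other side has substance. Phase II is exploratory with no hypotheses (7.1). Its objective is a numerical comparison with placebo (2.1.1), and the visible text contains no i.v.-versus-i.v. contrast or trend test, so the ordering figures concern a comparison the plan does not specify. Randomisation keeps every arm comparison unbiased. The two covariates already used are related to stage of infection. Onset time is an estimate, which weakens it as a covariate, and the variance share it would explain is assumed. All of this stands and limits the size of the point.

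Four stronger readings are tempting, and the documents do not support them.

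- *That delay governs response across the enrolment window.* 4.1.2 contrasts dosing at onset with later dosing; it gives no gradient over days 0 to 5.
- *That the model predicts no dose-response at all.* It says less sensitive and possibly comparable, for the two i.v. levels only. It says nothing of the kind about active versus placebo, the inhaled arm or exposure-response. For variants, IC50 values were also "scanned across a range from 1.5 to 15000 ng/mL". A flat i.v. response would still be usable under the lowest-efficacious wording.
- *That the interval is left out of every Phase II analysis.* Section 7.2.5 is not in the public text, and SAP section 4 lists dropping subgroup analyses as a change, so some had been planned. Only omission from the primary model can be confirmed.
- *That early and late treatment should be reported as separate ratios.* No passage says activity is expected mainly in early-treated patients. An assumed even split to 25 per arm would raise the probability of a ratio above 1.4 under no difference from about 2.4% to 8%, and lower power from 85% to 77%.

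**Conclusion.** The point holds as a modest improvement to the primary model plus a reconciliation of wording. The Phase II ANCOVA omits a recorded baseline variable that the protocol's own model ties to the size and dose-sensitivity of response. No bias results. The expected gain is an SE about 2.5 to 8% smaller, worth 5 to 18% more patients, if the interval explains 5 to 15% of residual variance. That share is an assumption; the documents give no figure for it. The probability of clearing the 1.4 threshold would move only from about 85% to 85 to 87%.

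The aim in 3.2 conflicts with 4.1.2, and its selection wording conflicts with the synopsis and 1.3. On the calibrated SD, two i.v. arms of about 50 can resolve only differences of roughly 29 to 37% of the active mean, so their numerical order says little about dose-response.

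This concerns the protocol as designed. With five patients randomised and no model to be fitted (SAP section 4), it does not alter the reported analysis.

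**What to change.** In 7.2.3, add days from symptom onset to dosing, as a continuous covariate, to the Phase II ANCOVA for the 8-day endpoint; 7.2.4 carries it to the 29-day endpoint. Align the synopsis, which names only baseline viral load as covariate.

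Reconcile 3.2 with 4.1.2 on what Phase II can show about dose-response, and state that a numerical ordering of the two i.v. arms is weak evidence of it. Reconcile the regimen-selection wording in 3.2 with that in the synopsis and 1.3, and the units printed in 4.1.2 with the rest of the protocol. Which selection rule applies is for the sponsor to settle.

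The cost is one degree of freedom, no new data collection, no extra patients and a few lines of text. The SAP needs no change while its analysis stays descriptive.
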